4.1.2. Exclusion criteria

Patients meeting any of the following criteria will not be included in the study:

- 1. Having a diagnosis of valvular atrial fibrillation, post-operative atrial fibrillation, rheumatic atrial fibrillation or mechanical-valvular atrial fibrillation during the baseline and post-index period
- 2. Having a cardiac surgery procedure record during the baseline period
- 3. Having a joint replacement procedure record during the baseline period
- 4. Having a procedure of prosthetic heart valve during the baseline period
- 5. Having a diagnosis of venous thromboembolism during the baseline period
- 6. Female patients with pregnancy during the follow-up period
- 7. Patients prescribed "off-label" doses of OACs (per Japanese package insert of each OAC) or patients treated with OAC but in "off-label" or "contraindicated" manners.

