9. RESEARCH METHODS

9.1. Study design

This is a retrospective non-intervention observational study to evaluate the difference in safety and effectiveness between apixaban and warfarin using a database provided by Medical Data Vision Co. Ltd. (MDV Co. Ltd.). Eligible patients will be extracted from the database and allocated to the pre-defined cohorts based on the actual age, age of NVAF diagnosis and types of anticoagulant therapy.

Based on the age category and anticoagulants on the index date (a date when patients initiated an anticoagulant for prevention of stroke/SE), eligible patients will be allocated to some cohorts. Patient characteristics will be balanced by an Inverse probability of treatment weighting (IPTW) method, and risk of stroke/SE (primary effectiveness endpoint) and major bleeding (primary safety endpoint) will be compared. Hazard ratios and 95% confident intervals will be calculated by using a COX proportional hazard method.

The following definitions will be used here

• Index date: the date when warfarin or apixaban was initiated

• Baseline period: the 180 days before the index date

• Cohorts:

- > Apixaban cohorts: patients who started an anticoagulant therapy with apixaban
- > Warfarin cohorts: patients who started an anticoagulant therapy with warfarin

• Observational period:

Follow-up period starts from the next day of the index date and ends depending on following outcomes which observed first.

- 1. Major bleeding when the target outcome for the analysis is major bleeding.
- 2. Composite of (ischemic or hemorrhagic) stroke and SE when the target outcome for the analysis is the composite endpoint.
- 3. Any bleeding when the target outcome for the analysis is any bleeding.
- 4. Discontinuation of the index OAC: The index treatment will be "discontinued" if the index OAC is not prescribed within 45 days after prescription refill date (calculated from the last refill date plus days of supply) of the index OAC, even though the patient has >1 medical encounter records after more than 45 days following the prescription refill date. The supposed prescription refill date is regarded as the last day of the follow-up for discontinued patients.

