4. ANALYSIS SETS/POPULATIONS

4.1. FULL ANALYSIS SET

4.1.1. Inclusion criteria

Patients must meet all the following inclusion criteria to be eligible for inclusion in the study.

1. Diagnosed with AF anytime in the baseline period or on the index date, also have definitive diagnosis of AF anytime in the baseline period, on the index date, or post-index period.

PFIZER CONFIDENTIAL

Page 7 of 51

- 2. Prescribed apixaban or warfarin on or after the day of AF diagnosis. The first observed prescription will be used to identify the patient's index date and treatment cohort
- 3. No use of the any OACs during the baseline period (the 180 days before the index date)
- 4. Age of 18 years or older on the index date.
- 5. Index date is at age 80 or older

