10.3. APPENDIX 3: DIAGNOSIS AND PROCEDURE CODES USED IN THE STUDY

10.3.1. List of diagnosis code

Variable Used in Study	ICD-10 Code [*]	Additional rules on Data Extraction
Atrial fibrillation	148	
Post-operative atrial fibrillation	8847772	Standard disease code
Valvular atrial fibrillation	8846941	Standard disease code

PFIZER CONFIDENTIAL

Variable Used in Study	ICD-10 Code [*]	Additional rules on Data Extraction
Rheumatic atrial fibrillation	105	
	106	
	107	
	108	
	109	
Mechanical-valvular atrial fibrillation	T820	
Hyperthyroidism or thyrotoxicosis	E05	
Heart failure	1110	
	1500	
	1501	Exclude cardiac asthma
	1509	
Hypertension	H208	Include only hypertensive iridocyclitis
	H350	Include only hypertensive retinopathy and hypertensive neuroretinopathy
	110	
	l110	
	I119	
	l120	
	1129	Include only hypertensive renal disease, hypertensive nephropathy and hypertensive nephrosclerosis
	1139	
	1150	
	1151	
	1152	
	1158	
	1159	
	l619	Include only hypertensive intracerebral hemorrhage
	1674	
Diabetes	E10	
	E11	
	E12	
	E13	
	E14	
Hemorrhage stroke	160	
	l61	
	162	Exclude non-traumatic extradural haemorrhage

Page 24 of 51

Variable Used	ICD-10	Additional rules
in Study	Code*	on Data Extraction
Ischemic stroke	163	
	3489032	standard disease code
	4371003	
	4379014	
	3448002	
	3448028	
	3489029	
	3489035	
	4379006	
TIA	H340	
	G450	
	G451	
	G458	
	G459	
Systemic embolism	1740	Include only abdominal aortic embolism
	1741	Include only aortic embolism
	1742	Include only acute arterial occlusive disease of arteries of upper extremities
	1743	Include only femoral arterial occlusion and acute arterial occlusive disease of arteries of lower extremities
	1744	
	1745	Include only iliac artery embolism
	1748	Include only hepatic artery embolism
	1749	Include only thromboembolism, embolic infarction, aortic embolism
Peripheral vascular disorder	1702	Include only atherosclerosis and arteriosclerosis obliterans
	1709	
	1731	Include only Buerger's disease
	1739	Exclude peripheral circulatory failure, cerebrovascular spasm, and angiospasm pf the extremities
	1742	
	1743	
	1745	
	1748	Include only subclavian artery stenosis
Aortic plaque	4400011	Standard disease code
	8837393	Standard disease code
Coronary artery disease	1200	

Page 25 of 51

Variable Used	ICD-10	Additional rules
in Study	Code [*]	on Data Extraction
	1208	
	1209	
	1200	
	1210	
	1212	
	1212	
	1214	
	1240	
	1210	
	1248	
	1210	
	1252	Exclude calcification of coronary artery
	1252	
	1258	Exclude coronary arteritis

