10.3.2. List of procedure code

Procedure	Procedure Code
Cardiac surgery	150138210
	150138310
	150138410
	150138510
	150359210
	150138710
	150140510
	150140610
	150140710
	150139010
	150140810
	150318010
	150317810
	150318110
	150331450
	150331550
	150331950
	150332050
	150317910
	150318210
	150140010
	150139210
	150153910
	150374910
	150375010
	150375110
	150260350
	150284310
	150359310
	150263310

PFIZER CONFIDENTIAL

Procedure	Procedure Code
	150375210
	150375310
	150375410
	160107550
	150139810
	150139910
	150318310
	150145710
	150145810
	150145910
	150146010
	150318410
	150318510
	150302770
	150143010
	150143110
	150331650
	150332150
	150318710
	150319010
	150319310
	150318810
	150319110
	150319410
	150328750
	150328850
	150331750
	150331850
	150332250
	150332350
	150318910
	150319210
	150319510
	150318610
	150141010
	150279510
	150279610
	150141410

Page 33 of 51

Procedure	Procedure Code
	150141610
	150369950
	150141710
	150359470
	150143610
	150260050
	150143710
	150143810
	150141510
	150375570
	150375670
	150375770
	150319610
	150292910
	150139310
	150140910
	150242550
	150244910
	150245010
	150359510
	150359610
	150381150
	150381250
	150381350
	150381450
	150150010
	150381550
	150275910
	150359710
	150359810
	150359910
	150381650
	150381750
	150381850
	150381950
	150150110
	150382050
	150245110

Page 34 of 51

Procedure	Procedure Code
	150245210
	150375870
	150375970
	150376070
	150141210
	150301310
	150267850
	150319710
	150151810
	150376110
	150139110
	150319810
	150138810
	150151910
	150320010
	150346410
	150320110
	150147150
	150144110
	150320210
	150320310
	150142710
	150139410
	150320410
	150142910
	150320510
	150260150
	150346510
	150145110
	150145010
	150376210
	150376310
	150143250
	150143350
	150143450
	150143550
	150283250
	150283350

Page 35 of 51

Procedure	Procedure Code
	150283450
	150283550
	150144910
	150139610
	150142410
	150141810
	150141910
	150320610
	150142050
	150142110
	150142210
	150142310
	150142810
	150144010
	150320710
	150144210
	150144550
	150147410
	150147510
	150320810
	150320910
	150144410
	150144650
	150144750
	150146510
	150146610
	150321010
	150321110
	150321210
	150376470
	150146910
	150146810
	150321310
	150142510
	150329810
	150145310
	150329910
	150139510

Page 36 of 51
Procedure	Procedure Code
	150330010
	150147010
	150330110
	150376570
	150321410
	150321510
	150376670
	150147310
	150145650
	150141310
	150321810
	150321610
	150321910
	150146710
	150321710
	150330210
	150330310
	150376770
	150293010

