	150330410
	150145510
	150302870
	150145410
	150322010
	150322110
	150144310
	150147250
	150346610
	150144810
	150253810
	150253910
	150275610
	150346710
	150262810
	150303310
	150267310
	150140110
	150140210

Page 37 of 51

Procedure	Procedure Code
	150140410
	150346910
	150347010
	150303210
	150322210
	150275210
	150275310
	150336910
	150337010
	150360010
	150148010
	150148110
	150147610
	150147910
	150147770
	150147870
	150347170
	150275870
	150262910
	150275710
	150266110
	150382650
	150266210
	150382750
	150301810
	150382850
	150303410
	150303510
	150360110
	150360210
	150360310
	150360410
	150303610
	150303710
	150322410
	150322610
Ablation	150346710
	150262810

Procedure	Procedure Code
	150303310
	150346870
	150370050
Electrical defibrillation	140051410
	140010310
	140055010
	150275210
	150275310
	150336910
	150337010
	150370550
Heart valve prosthesis implantation surgery	150141410
	150141610
	150141710
	150359470
	150369950
	150331950
	150332050
	150332150
	150328850
	150332250
	150332350
	150141510
	150375570
	150375670
	150375770
	150244910
	150359510
	150381150
	150381250
	150359710
	150359810
	150381650
	150381750
	150283450

Page 39 of 51

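### As coded, the prosthetic-valve exclusion removes no patient that the cardiac-surgery exclusion does not already remove, and neither rule sees a valve procedure recorded more than 180 days before index

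*SAP*

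**What the plan says.** The exclusion criteria are the same in SAP 4.1.2 and Protocol 9.3.2. Three of them bear on valves:

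- Criterion 1 removes recorded diagnoses of valvular, post-operative, rheumatic or "mechanical-valvular atrial fibrillation during the baseline and post-index period".
- Criterion 2 removes patients "Having a cardiac surgery procedure record during the baseline period".
- Criterion 4 removes patients "Having a procedure of prosthetic heart valve during the baseline period".

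Protocol 9.1 fixes the window: "Baseline period: the 180 days before the index date". SAP 4.1.1, inclusion criterion 3, uses the same length.

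SAP 10.3.2 gives the procedure codes, with separate lists headed "Cardiac surgery" and "Heart valve prosthesis implantation surgery". SAP 10.3.1 gives the diagnosis codes. There, "Mechanical-valvular atrial fibrillation" is identified by T820 alone. Valvular and post-operative AF each have one standard disease code, and rheumatic AF has five whole ICD-10 categories.

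The propensity covariates in SAP 7.1.2.1 include no item for valve disease or a valve prosthesis.

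**The concern.** Criteria 2 and 3 concern recent operations, for which a 180-day window is natural. A prosthetic valve is different: it is still there after 180 days. The plan names it as a separate reason for exclusion but searches for it only as a recent procedure.

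The searches are also uneven. Criterion 1 follows a patient's valve-related diagnoses through the post-index period. No rule looks for a valve procedure in recorded history beyond 180 days before index. Patients are drawn from 26 February 2013 to 31 December 2021 (SAP 2.1.1), so some may have years of earlier records.

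What is at stake is first whether the cohort matches its label, non-valvular AF. Second, if retained valve patients were unequally divided between apixaban and warfarin and had different event rates, both primary comparisons would be affected. Weighting could not balance valve status directly, because the model has no term for it. The E-values in SAP 7.2.3 address unmeasured confounding in general and would not identify these patients.

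**Working it through.** **Step 1: do the code lists overlap?** Inputs are the lists in SAP 10.3.2.

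| List | Distinct codes | Not in the cardiac-surgery list |
|---|---|---|
| Cardiac surgery | 256 | – |
| Heart valve prosthesis | 24 | 0 |
| Ablation | 5 | 2 |
| Electrical defibrillation | 8 | 4 |

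All 24 valve codes are contained. The last two rows show that the cardiac-surgery list is not a catch-all that would contain any cardiac procedure list.

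**Step 2: are the windows the same?** Criteria 2 and 4 both use the baseline period of 180 days. A patient is excluded on meeting any one criterion. With the same window and contained codes, every patient caught by criterion 4 is also caught by criterion 2. Additional patients removed by criterion 4 = 0.

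**Step 3: what happens to an earlier valve?** Take a valve procedure recorded 8 months before index. It is outside the window of criteria 2 and 4. The patient can still be removed by:

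- exclusion 1, if a valvular, post-operative, rheumatic or T820 diagnosis is recorded in the baseline or post-index period;
- inclusion 3, if any OAC is recorded in the prior 180 days;
- exclusion 7, if treatment is judged off-label or contraindicated (the visible text gives no code or algorithm for this).

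A patient who meets none of these stays in. The documents give no count of such patients in either cohort.

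**Step 4: how large could the effect be?** This cannot be computed. The following is an illustration on assumed inputs only. Let shares p_A and p_W of the apixaban and warfarin cohorts be retained valve patients, with event rate r times that of the others. The hazard ratio is then multiplied by roughly

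(1 + p_A(r − 1)) / (1 + p_W(r − 1)).

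With r = 2 and all such patients in one cohort, applied to the planning hazard ratios of SAP 4.5 (0.59 major bleeding, 0.53 stroke/SE):

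| Share p | All in warfarin, 1/(1+p) | HRs become | All in apixaban, 1+p | HRs become |
|---|---|---|---|---|
| 1% | 0.990 | 0.584; 0.525 | 1.01 | 0.596; 0.535 |
| 2% | 0.980 | 0.578; 0.520 | 1.02 | 0.602; 0.541 |
| 5% | 0.952 | 0.562; 0.505 | 1.05 | 0.620; 0.557 |

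If the shares are equal, the multiplier is 1.

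**The case against.** **Redundancy alone does no harm.** Overlapping exclusions change no result. Inclusion 4 (18 or older) is equally idle beside inclusion 5 (80 or older). This stands: the overlap is only a sign that criterion 4 does not do a job of its own. The substance is the missed earlier procedure.

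**The window may be deliberate.** Criteria 2 to 5 all use the baseline period, and the documents do not define NVAF for every type of prosthesis. This stands in part. But the authors gave prosthetic valves a separate line without limiting the type, and neither document gives a reason for ignoring an older one.

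**Other rules already protect the cohort.** A reader might infer that T820 is the only remaining guard. The documents do not support that. Exclusion 1 has four diagnoses and runs through the post-index period, and inclusion 3 removes patients with an older valve whose anticoagulation is visible in the database. The group left is therefore narrow. It is not shown to be empty: each diagnosis must be coded in the window, and prescriptions issued outside the participating hospitals may not be visible (an inference from the hospital-based source in Protocol 9.6).

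**The bias has no known direction.** A reader might infer that retained valve patients collect in the warfarin cohort and tilt the result towards apixaban by 1% to 5%. Nothing in the documents supports the one-sided allocation, the doubled rate or the shares. Exclusion 7 could act differently on the two drugs, but the text does not show that it does. This objection stands in full.

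**A longer look-back brings its own unevenness.** Later index dates can have more history, and the SAP recognises that treatment choice changes with calendar time. This stands as a cost. Estimating propensity scores by calendar year should limit it, though consecutive years may be pooled.

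**Conclusion.** The point holds in a limited form. It is certain from the documents that criterion 4 removes no patients beyond criterion 2, and that a valve procedure recorded more than 180 days before index is missed by both. Such a patient can enter the non-valvular AF cohort unless exclusion 1, inclusion 3 or exclusion 7 intervenes, and the propensity model has no valve term.

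The number of such patients, and the size and direction of any bias, are not known. The effect is probably small: even the one-sided, doubled-rate assumptions above move the planning hazard ratios by no more than about 5% in either direction, leaving them well below 1. That judgement rests on the retained share being a few per cent at most, which the sponsor can check and the documents cannot show. The reason to act is that the population should match its label and that the criterion should do what it appears to promise.

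**What to change.** In SAP 4.1.2 and Protocol 9.3.2:

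1. Reword criterion 4 to a prosthetic-valve procedure record at any time in the available data on or before the index date, using the 24 codes already listed.
2. In criterion 1, extend the search for the mechanical-valvular AF code (T820) back over the same history, in addition to the existing baseline and post-index window and not in place of it.
3. Leave criteria 2 and 3 at 180 days.
4. Report the number of patients removed per cohort by the wider look-back, and both primary hazard ratios with and without it. This replaces the assumptions above with observed figures.

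The cost is a changed phrase in each document, a wider date filter and one extra pair of estimates. The documents do not say how far back the extract reaches, so the sponsor should confirm that it holds the earlier procedure and diagnosis records. The downside is a look-back that varies between patients and with index year, and slightly fewer eligible patients. Stating the available pre-index history by cohort and index year would let readers judge the first of these.

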4.2. Study hypothesis and clinical questions

The ARISTOTLE study and various real-world evidence (RWE) have shown that apixaban is superior or equivalent to warfarin in safety and effectiveness profile. Subgroup analyses of the ARISTOTLE study suggested that superiority over warfarin could be consistent in most populations including high risk populations. Study hypothesis and clinical questions in this study is apixaban is superior to warfarin in both safety and effectiveness even in the very elderly patients with NVAF in the real-world settings.

The clinical question of this study is that apixaban has a superior effectiveness and safety profile compared to warfarin, even in very elderly patients who are at particularly high risk, such as those with CCI , frail or frail patients, CCI

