9.3.2. Exclusion criteria

Patients meeting any of the following criteria will not be included in the study:

- 1. Having a diagnosis of valvular atrial fibrillation, post-operative atrial fibrillation, rheumatic atrial fibrillation or mechanical-valvular atrial fibrillation during the baseline and post-index period
- 2. Having a cardiac surgery procedure record during the baseline period

- 3. Having a joint replacement procedure record during the baseline period
- 4. Having a procedure of prosthetic heart valve during the baseline period
- 5. Having a diagnosis of venous thromboembolism during the baseline period
- 6. Female patients with pregnancy during the follow-up period
- 7. Patients prescribed "off-label" doses of OACs (per Japanese package insert of each OAC) or patients treated with OAC but in "off-label" or "contraindicated" manners.

| CCI | | | |
|-----|---|--|--|
| | | | |
| | I | | |
| | | | |
| | | | |
| | | | |
| | C | | |
| | I | | |
| | | | |
| | | | |
| | I | | |
| | | | |
| | | | |
| | | | |
| | | | |
| | | | |
| | | | |
| | | | |

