5.4. COVARIATES

Items	definitions	roles
Gender	Male or female	Patient characteristics
		CCI
Body weight	≥ 60 kg or < 60 kg	Patient characteristics
eGFR (continuous)	Value in the baseline If a patient has multiple eGFR values, the values closest to the index date will be adopted	Patient characteristics
eGFR (categorical)	≥ 50 ml/min or < 50 ml/min	Patient characteristics
Serum creatinine (continuous)	Value in the baseline If a patient has multiple eGFR values, the values closest to the index date will be adopted	Patient characteristics

PFIZER CONFIDENTIAL

Serum creatinine (categorical)	≥ 1.5mg/mL or < 1.5	Patient
	mg/mL	characteristics
CHADS2	CHADS2 score will be calculated based on age and the presence of congestive heart failure, hypertension, diabetes, and stroke or TIA.	Patient characteristics
CHA2DS2-VASc	CHA2DS2-VASc score will be calculated based on age and the presence of congestive heart failure, hypertension, diabetes, stroke or TIA, vascular disease and sex category.	Patient characteristics
CCI		

Page 13 of 51

	CCI	
Medications		
CCI		
Treated with antiplatelet drug in baseline	Defined using prespecified drug- specific codes: Yes or No	Patient characteristics
PFIZER CO	NFIDENTIAL	

Page 14 of 51

		I
Treated with NSAIDs in baseline	Defined using prespecified drug- specific codes: Yes or No	Patient characteristics
Treated with gastric secretion inhibitor in baseline	Defined using prespecified drug- specific codes: Yes or No	Patient characteristics
Treated with statin-based drug in baseline	Defined using prespecified drug- specific codes: Yes or No	Patient characteristics
Treated with anti-hypertensives in baseline	Defined using prespecified drug- specific codes: Yes or No	Patient characteristics
Treated with anti-arrhythmics in baseline	Defined using prespecified drug- specific codes: Yes or No	Patient characteristics
Treated with beta-blockers in baseline	Defined using prespecified drug- specific codes: Yes or No	Patient characteristics
Procedures		
Cardioversion	Defined using prespecified medical procedure codes: Yes or No	Patient characteristics
Cardiac ablation	Defined using prespecified medical procedure codes: Yes or No	Patient characteristics
Anticogulation		
INR (warfarin cohort)	Continuous variable. * Only available for patients treated with warfarin	Patient characteristics
Apixaban doses	2.5 mg BID or 5mg BID * Only available for patients treated with apixaban	Patient characteristics

Chronically prescribed medicines

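### Exclusion criterion 7 is naturally read as a test against the label of the drug received, so patients barred from one drug only can stay in the other arm with no counterparts

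*SAP*

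**What the plan says.** Criterion 7 has the same wording in SAP 4.1.2 and Protocol 9.3.2, and it has two limbs, joined in one sentence that excludes patients on off-label "doses of OACs (per Japanese package insert of each OAC) or patients treated with OAC but in" an off-label or contraindicated way. The dose limb excludes patients whose dose is off-label, judged "per Japanese package insert of each OAC". The manner limb excludes patients treated with an OAC in an off-label or contraindicated way, and names no insert.

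The arm is set by the drug first prescribed (SAP 4.1.1): "The first observed prescription will be used to identify the patient's index date and treatment cohort".

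The other visible criteria (AF diagnosis, age, no recent OAC, surgery, valve procedure, venous thromboembolism, pregnancy) do not refer to which of the two drugs was given. No visible criterion requires a patient to be eligible for both drugs.

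SAP 5.4 records apixaban dose as "2.5 mg BID or 5mg BID". For INR it notes: "Only available for patients treated with warfarin". The appendix of codes contains no list for criterion 7, and Appendix 1 on data derivation is marked not applicable. The only planned sensitivity analysis is the E-value (SAP 7.2.3).

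**The concern.** Eligibility should not depend on treatment in a comparison of two drugs. Take two identical patients with a condition that only drug A's insert lists as a contraindication. The one given A is removed and the one given B stays. This patient type then exists in one arm only.

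The planned methods do not repair this. Stabilised weights re-weight the patients who are present; they cannot create a counterpart that the exclusion rule has deleted. The balance check (standardised difference below 10%) and the fallback adjustment in the Cox model look only at measured variables. The E-value says how strong an unmeasured confounder would have to be; it does not restore the missing patients.

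Both primary hazard ratios are at stake. The hypothesis (Protocol 4.2) is superiority of apixaban on safety and effectiveness "even in the very elderly patients with NVAF in the real-world settings". If the retained patients are at high risk and sit in the warfarin arm, the ratios move toward that hypothesis. If they sit in the apixaban arm, the ratios move away from it.

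**Working it through.** **1. The wording.** The dose limb can only be applied to the drug prescribed. The manner limb speaks of patients treated with an OAC, so its natural object is also the drug prescribed. SAP 4.1.1 makes that same drug the arm. A condition in one insert but not the other therefore removes patients from one arm only. A condition in both inserts removes them from both arms and does no harm. The problem exists only where the inserts differ.

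**2. Size, by assumption.** The documents give neither the insert conditions nor their frequency, so p and r below are assumed.
- p: share of the raw warfarin arm barred from apixaban only
- r: their event-rate ratio against other warfarin patients, after adjustment for the propensity-score variables
- q: their share of the weighted warfarin arm

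Treating the hazard ratio as a ratio of rates, the warfarin rate is multiplied by 1 + q(r − 1), so

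observed HR = true HR / (1 + q(r − 1)).

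The value of q depends on what the propensity score sees.
- If it does not identify these patients, q = p.
- If it identifies them fully, their apixaban propensity is near 0 and their stabilised weight is near P(warfarin). SAP Table 1 gives 62,453 / (76,260 + 62,453) = 62,453 / 138,713 = 0.45. Stabilised weights average about 1 in the arm, so q is about 0.45p. These counts precede all eligibility criteria, so 0.45 is approximate.

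For a true HR of 1.00:

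| p | r | Not identified | Fully identified |
|---|---|---|---|
| 2% | 2 | 1/1.02 = 0.98 | 1/1.009 = 0.99 |
| 5% | 3 | 1/1.10 = 0.91 | 1/1.045 = 0.96 |
| 10% | 3 | 1/1.20 = 0.83 | 1/1.09 = 0.92 |

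**3. Against the planning hazard ratios** (SAP 4.5: 0.59 for major bleeding, 0.53 for stroke/SE), at p = 5%, r = 3:
- 0.59 reads 0.59/1.10 = 0.54 to 0.59/1.045 = 0.56
- 0.53 reads 0.53/1.10 = 0.48 to 0.53/1.045 = 0.51

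**4. The other direction.** If the share p sits in the apixaban arm (barred from warfarin only), the observed HR is the true HR × (1 + q(r − 1)). The weight under full identification is 76,260/138,713 = 0.55. A true 1.00 then reads 1.055 to 1.10 at p = 5%, r = 3, and 1.11 to 1.20 at p = 10%, r = 3.

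**5. Room for a stricter rule.** SAP Table 2 reproduces with the two-sided 5%, 80% power Schoenfeld formula at 1:1, dividing events by the mean annual rate:
- major bleeding: 113 events; 113 / ((0.025 + 0.0118)/2) = 113/0.0184 = 6,141
- stroke/SE: 78 events; 78 / ((0.0192 + 0.0098)/2) = 78/0.0145 = 5,379

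These are 4.4% and 3.9% of the 138,713 patients counted before criteria. A common rule changes none of these inputs.

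**The case against.** The effect exists only if the two inserts differ, and neither is in the documents. Size and sign therefore cannot be established. This stands.

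The reference to each OAC's insert qualifies only the dose limb; that the manner limb means the drug received is an inference. This also stands, though it is the natural reading and nothing visible offers another. Criterion 7 has no codes or look-up window, so the programmed rule could differ from the text. Protocol 9.4 and SAP 4.4 are blacked out, so a both-drugs rule there cannot be ruled out.

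The propensity score is fairly rich: age, stroke/SE, bleeding, heart failure, hypertension, renal and liver diagnoses, antiplatelets, NSAIDs, heparins and the risk scores. Part of the excess risk is thus adjusted, which is why r must be a residual ratio. An r of 3 is at the high end.

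Limiting the study to on-label use is a declared choice, and routine-care data restricted in this way still address a real-world question. This too is fair. The issue is that the restriction may differ by arm.

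A reader might infer more than this:
- That label-conforming apixaban is compared with nearly all warfarin use. The manner limb also removes warfarin patients treated off-label or against a contraindication.
- That the dose limb removes mainly apixaban patients, because two fixed apixaban doses are recorded and no warfarin dose is. SAP 5.4 is a table of patient characteristics, not of the data used for exclusions, so it does not show that warfarin dosing goes unchecked.
- That severe renal or liver disease is the contraindication at issue. No passage says so.

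**Conclusion.** The point holds as a matter of design. On its natural reading, criterion 7 makes eligibility depend on the drug received. Patients barred from one drug only are then missing from that arm by rule, and neither the weights nor the E-value can put them back.

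Its size is not known. Under the assumed p and r, a true HR of 1.00 reads 0.91 to 0.96 (5%, r = 3) or 0.83 to 0.92 (10%, r = 3) if the retained patients are on warfarin, and moves above 1 by a similar order if they are on apixaban. If the true effects are as strong as the planning values, a shift of this kind would not change the direction of the conclusion. It matters if the true ratio is near 1. With cohorts as large as the feasibility counts suggest, random error may be small, so a systematic shift of this order could then drive the result.

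A reader might conclude that the rule favours apixaban. The documents do not support any statement on net direction. The change is worth making because it is specific and cheap and removes the dependence whichever way it runs.

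**What to change.** - Reword criterion 7 in the SAP and protocol so that one common set of contraindications applies to every patient whichever drug was prescribed, assessed on records up to and including the index date. The sponsor draws the set from both inserts; its clinical content is for the sponsor to define.
- Report the number excluded under criterion 7 by arm and by limb (dose, manner).
- The dose limb can only be applied to the drug received, so repeat both primary hazard ratios with patients excluded by that limb kept in.
- If Protocol 9.4 or SAP 4.4 already contains a both-drugs rule, cross-reference it in criterion 7.

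Cost: code lists for both inserts must be compiled, since none appears in the visible appendix; some patients are lost from the arms; and the two primary models are run once more. The margin over the 6,141 and 5,379 patients required suggests that the loss of numbers is not a serious obstacle, although the number itself cannot be computed from the documents.
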